14.2 Populations for Analyses

The following populations will be defined for this study:

Safety population: will include all enrolled patients who received any quantity of study treatment, regardless of their eligibility for the study.

Efficacy Population: will include all enrolled patients who received any quantity of study treatment, regardless of their eligibility for the study.

Biomarker population: will include the subset of patients from the safety population from whom a valid assay results have been obtained.

14.3 Statistical Analyses

Statistical analysis of this study will be the responsibility of Indiana University Department of Biostatistics or its designee. Any change to the data analysis methods described in the protocol will require an amendment only if it changes a principal feature of the protocol. Additional exploratory analyses of the data will be conducted as deemed appropriate.

14.3.1 Safety Analyses

For safety analyses, CTCAE Version 5.0 will be used to summarize adverse events in the assessment of safety for incorporating LY3214996 in combination with abemaciclib. Summaries of treatment related adverse events in the population will be tabulated. All adverse events (AEs) will be presented in incidence tables coded by CTC term. An adverse event will be considered treatment related if it occurred on or after date of first dose of LY3214996 or abemaciclib and was possibly, probably, or definitely related to treatment. All adverse events will be recorded

until off study date. All deaths recoded in this study will be listed and summarized, and the cause documented.

14.3.2 Efficacy Analyses

14.3.2.1 Endpoints

Overall response rate is defined as the number of patients who achieve a best overall response of complete response (CR) or partial response (PR) divided by the total number of patients treated (efficacy population).

Progression-free survival (PFS) is defined as the time from the date of start of treatment to the first date of the observed clinical or radiologically documented PD or death due to any cause, whichever occurs first. For patients who are not known to have died or progressed as of the data-inclusion cut-off date, PFS time will be censored at the date of the last objective progression-free disease assessment prior to the date of any subsequent systematic anticancer therapy.

The duration of overall response is measured from the time measurement criteria are met for CR or PR (whichever is first recorded) until the first date that recurrent or progressive disease is objectively documented (taking as reference for progressive disease the smallest measurements recorded since the treatment started).

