9.1 Discontinuation from Study Treatment

Patients will be discontinued from study treatment in the following circumstances:

- the patient is enrolled in any other clinical trial involving an investigational product or any other type of medical research judged not to be scientifically or medically compatible with this study
- the patient becomes pregnant during the study
- the patient is significantly noncompliant with study procedures and/or treatment
- disease progression

- If a patient is clinically stable at the first radiologic progressive disease by RECIST v1.1 (Eisenhauer et al. 2009), the patient may be considered for continuation on the study until progression is confirmed. For patients to be considered for continuation the following criteria must all be met, and after consultation with the Principal Investigator:
 - Absence of symptoms and signs indicating clinically significant progression of disease
 - No decline in ECOG performance status
 - Absence of symptomatic rapid disease progression requiring urgent medical intervention (e.g. symptomatic pleural effusion, spinal cord compression).
- Treatment beyond progression must not delay an imminent intervention to prevent serious complications of disease progression (e.g., central nervous system metastases).
- Subjects' clinical data must be available for CRF source verification. Copies of tumor images must be made available for review by the sponsor or its designee upon request.
- unacceptable toxicity
- the patient, for any reason, requires treatment with another therapeutic agent that has been demonstrated to be effective for treatment of the study indication. Discontinuation from study treatment will occur prior to introduction of the new agent.
- the investigator decides that the patient should be discontinued from study treatment
- the patient requests to be discontinued from study treatment
- the patient's designee (for example, parents, legal guardian, or caregiver) requests that the patient be discontinued from study treatment

Patients are considered to have discontinued from study treatment when all study treatments are no longer administered. Based on investigator discretion and/or patient preference, patients may continue on study treatment while taking either LY3214996 or abemaciclib alone. Patients who are discontinued from study treatment will have follow-up procedures performed as shown in the Schedule of Activities (Section 2).

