14.1 Sample Size Determination

The primary end point is overall response rate (ORR), where overall response is defined as the complete or partial response per RECIST criteria. We will use the one stage design for the phase II trial. We will use the one stage design to test the null hypothesis that the true ORR is 5% versus the alternative hypothesis that that the true ORR is 19% using a one-sided test with the designing parameters type-I error=0.05 and type II error=0.2 (power=80%).

A total sample size of 28 evaluable patients will be accrued. The trial is considered a success when the null hypothesis is rejected, which is determined when 4 or more patients have an overall response among the 28 patients. Of note, an evaluable patient is defined as a patient who receives at least one dose of the study drug. Assuming a 20% drop-out rate, it is anticipated that the total accrual would be 35 patients.

We will add additional early stopping rules for the following subgroups of patients with pathogenic alterations in 1) BRAFV600E 2) BRAF nonV600E, RAF1 3) MEK1/2, ERK1/2 and 4) NF1. We will use the Bayesian posterior probability to monitor the response rates for those subgroups. A beta distribution of Beta (0.05,0.05) is assigned as the prior. Then, when every 5 evaluable patients have been enrolled in the specific subgroup under monitoring, we will calculate the posterior probability that the ORR rate for that subgroup is less than 5%. If this posterior probability is greater than 90% during any interim analysis, we will claim that the drug is not promising for this subgroup and will stop any future enrollment for that subgroup of patients. That is, for the 5th, 10th, 15th, 20th, 25th, 30th, and 35th patients in the subgroup, we will determine the enrollment for that subgroup if none of the patients report as tumor response. If the early stopping rule has been triggered, then at the end of the trial we will exclude all the patients in that subgroup from final analysis. We will use a binomial exact test to test the effectiveness of the drug for the remaining patients.

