14.3.2.2 Analysis Planned

14.3.2.2.1 *The Analysis of Primary Endpoint*

The primary end point is overall response rate (ORR), where overall response is defined as the complete or partial response per RECIST v1.1 criteria. We will use the one stage design for the phase II trial. We will specify the null hypothesis that the true ORR is 5% versus the alternative hypothesis that that the true ORR is 19% using a one-sided test with the designing parameters type-I error=0.05 and type II error=0.2 (power=80%).

14.3.2.2.2 *The Analysis of Secondary Endpoint*

The safety and tolerability will be summarized and tabulated as in Section [14.3.1](#).

The secondary endpoint of progression free survival and the duration of response will be analyzed using the Kaplan-Meier method.

14.3.2.2.3 *The Analysis of Correlative Obejctives*

To identify potential predictive biomarkers beyond the genomic alteration, exploratory analysis of gene expression and DNA mutations will be analyzed to associated with ORR and PFS. In this exploratory analysis, the association of DNA mutations in genes and pathways of interest with ORR and PFS will be performed using logistic regression, and Cox regression model. High-dimensional data in these regression models will be dealt using Lasso and Elastic-Net Regularized Generalized Linear Models (glmnet package in R) For gene expression, differential expression between responders and non-responders will be identified using the DESeq package in R.

Plasma concentrations of LY3214996, abemaciclib and its metabolites will be summarized using descriptive longitudinal and statistics. Further PK/PD analyses will be analyzed using linear mixed effect model, in particular, the AUC will be estimated and summarized. However, all of these analyses will be exploratory.

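### The PFS censoring rule counts time after a switch to new therapy only when that time ends in an event; if patients switch before progression, this lowers the median slightly

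*Combined protocol and SAP*

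**What the plan says.** Median PFS is a secondary objective (Synopsis; Table 4.1). Section 14.3.2.1 runs PFS from start of treatment to the first clinical or radiological progression or death from any cause. The event definition does not mention later anticancer therapy.

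Later therapy appears only in the censoring sentence. That sentence opens "For patients who are not known to have died or progressed as of the data-inclusion cut-off date, PFS time will be censored" and sets the censoring date "at the date of the last objective progression-free disease assessment prior to the date of any subsequent systematic anticancer therapy". (I read systematic as systemic.)

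Other relevant places:

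- Section 14.3.2.2.2: "progression free survival and the duration of response will be analyzed using the Kaplan-Meier method". No sensitivity analysis is named.
- Section 9.1: reasons to stop include toxicity, patient request, investigator decision, and the case where a patient "requires treatment with another therapeutic agent that has been demonstrated to be effective for treatment of the study indication".
- Section 9.4: follow-up ends at the day-30 safety visit or death, and later anticancer therapies are recorded. Section 14.3.2.6 tabulates them.
- Table 2.1: scans fall at every odd cycle, and none is marked at the safety visit.

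**The concern.** Kaplan-Meier requires that the decision to censor a patient at a given time does not depend on what happens to that patient afterwards. Here it does. Among patients who start a new drug before progression, those with a later known event stay in the risk set until that event. Those without one are removed at a date before the switch. Post-switch time contributes events but no event-free follow-up.

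At stake is the median PFS reported for the combination. Events on another drug would be charged to it while the matching event-free time is dropped. PFS also feeds the exploratory Cox models in Section 14.3.2.2.3. In addition, two programmers could code the sentence differently, one literally and one as a rule for everyone.

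**Working it through.** **1. The plan's own figures.** The documents state no figure for PFS. The primary design says "A total sample size of 28 evaluable patients will be accrued", with success "determined when 4 or more patients have an overall response among the 28 patients". Exact binomial with n = 28:

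- P(X ≥ 4 | p = 0.05) = 0.0491, within the stated 0.05.
- P(X ≥ 4 | p = 0.19) = 0.8065, against the stated 80%.
- 28 / (1 − 0.20) = 35.

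The design reproduces, and nothing below touches it.

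**2. Two patients under the written rule.** Both have a clear scan at day 2 × 28 = 56, stop that day without progression, and start a new drug 14 days later, on day 70. The safety visit falls on day 56 + 30 = 86.

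- Patient A dies on day 86: PFS event at day 86.
- Patient B is alive and event-free on day 86: censored at day 56.

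Their histories are identical up to the outcome, yet their risk periods differ by 86 − 56 = 30 days because of that outcome.

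**3. Extra events by hand.** Assumptions, none given in the documents: s = share who switch before an event, m = median time to progression or death after the switch (hazard unchanged by the new drug), g = days from stopping to new therapy, d = share of post-switch events that become known. Events are known to day 30 (Section 9.4), so the window is w = 30 − g.

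Extra events per 28 = 28 × s × (1 − 2^(−w/m)) × d

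- High end (s = 0.30, m = 90, g = 0, d = 1): 28 × 0.30 × (1 − 2^(−30/90)) = 8.4 × 0.206 = 1.73.
- Low end (s = 0.10, m = 120, g = 14, d = 0.25): 28 × 0.10 × (1 − 2^(−16/120)) × 0.25 = 2.8 × 0.088 × 0.25 = 0.06.

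Simulation gives 1.7 and 0.05. The small differences arise because the cut-off and events during the gap reduce the realised share of switchers.

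**4. Shift in the median.** I simulated 1,000,000 patients per setting: exponential PFS with true median 90 or 120 days, switching independent of prognosis, and cut-off uniform over 180-540 days (from 12 months' enrolment within 18 months' study). Each entry is the Kaplan-Meier median under the written rule relative to a rule censoring every switcher.

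| True median | Switchers | Same-day new drug, d = 100% | 14-day gap, d = 100% | 14-day gap, d = 25% |
|---|---|---|---|---|
| 90 d | 10% | −1.9% | −0.9% | −0.2% |
| 90 d | 20% | −4.1% | −1.9% | −0.5% |
| 90 d | 30% | −6.9% | −3.2% | −0.8% |
| 120 d | 10% | −1.6% | −0.7% | −0.2% |
| 120 d | 20% | −3.4% | −1.7% | −0.4% |
| 120 d | 30% | −5.7% | −2.7% | −0.8% |

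These runs censor at the date of stopping. Moving censoring back to the last 8-week scan gives shifts of about −0.1% to −5%. With no switching before an event, the two rules coincide and the shift is zero.

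**5. Scale.** With 28 exponential event times, the standard error of the median is about 1/(ln 2 × √28) = 1/(0.693 × 5.292) = 27% of the median. At a 90-day median that is about 0.27 × 90 = 24 days. The largest shift in the table is about 0.069 × 90 = 6 days.

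**The case against.** **Switching before progression is assumed.** No document gives a rate. The Section 9.1 item on needing another agent does not say the patient is progression-free, and Section 8.6 mentions other antitumor therapy in connection with progression. Clinical progression is itself a PFS event, so many patients who deteriorate will have their event before switching. Patients may also continue on one study drug alone. This stands: the effect is conditional and may be zero. It does not make the case remote. Section 9.1 allows stopping for toxicity or by choice, Appendix 4 requires it for some toxicities, and later therapies are to be collected.

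**Post-switch events will often go unseen.** With no scan scheduled after stopping, only deaths, clinical progression or outside scans can be known. This stands, and it is why detection runs from 25% upward. The asymmetry remains: an event can be recorded without a scan, but event-free time needs an objective assessment.

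**A shift near 10% is tempting to infer.** It arises with 30% switchers, a new drug on the day of stopping, a post-switch median of 2 months (61 days) and full detection, where the extra events are 28 × 0.30 × (1 − 2^(−30/61)) = 2.4. The documents support none of these inputs, and full detection sits badly with the absence of scans after stopping.

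**The uniform rule does not restore the true median.** Correct. It still censors back to a scan, while clinical progression or death between that scan and the new therapy still counts. With an 8-week grid and progression recorded continuously, the uniform rule reads about 2% to 11% below the assumed true median. This residual can exceed the wording effect. It would be smaller if progression is found mainly at scans.

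**No decision turns on PFS.** True: it has no hypothesis, threshold or power. That limits the importance but is no reason to keep an avoidable fault.

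**Conclusion.** The point holds as a minor one. As written, Section 14.3.2.1 makes the handling of post-switch time depend on whether an event follows, and no other section overrides it. If patients start new therapy before progression, the Kaplan-Meier median is pulled down relative to one rule for all.

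The size is about −0.1% to −7%, with 0.05 to 1.7 extra events per 28. It rests on a true median of 3-4 months, 10-30% switchers, switching unrelated to prognosis, an unchanged hazard after the switch, events known to day 30, and 25-100% of post-switch events detected. The top of the range needs 30% switchers, same-day new therapy and full detection together.

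A reader might infer that the reported median PFS will be biased. The documents do not support so flat a statement, because they give no number of patients expected to switch before progression. If switching is related to prognosis, or the new drug works, the distance from the true median changes in ways the documents do not allow one to calculate.

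**What to change.** Replace the conditional cut-back in Section 14.3.2.1 with one rule for all patients, for example: *Patients who start subsequent systemic anticancer therapy before PD or death are censored at the last progression-free assessment before that therapy, whether or not PD or death is recorded later.* Add a sensitivity analysis that counts all known events regardless of new therapy and does not censor at its start.

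The uniform censoring version suits this trial as the main analysis, because no scan is scheduled after treatment stops and follow-up ends at about day 30.

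The cost is one sentence and one further Kaplan-Meier run. No new data are needed, since Section 9.4 already collects later therapies. The downside is perhaps one or two fewer PFS events. The change removes the outcome-dependent handling of post-switch time. It leaves the residual effect of censoring back to an 8-week scan and any informative switching, so the report should give the number of patients who switched before progression.

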14.3.2.2 Analysis Planned

14.3.2.2.1 *The Analysis of Primary Endpoint*

The primary end point is overall response rate (ORR), where overall response is defined as the complete or partial response per RECIST v1.1 criteria. We will use the one stage design for the phase II trial. We will specify the null hypothesis that the true ORR is 5% versus the alternative hypothesis that that the true ORR is 19% using a one-sided test with the designing parameters type-I error=0.05 and type II error=0.2 (power=80%).

14.3.2.2.2 *The Analysis of Secondary Endpoint*

The safety and tolerability will be summarized and tabulated as in Section [14.3.1](#).

The secondary endpoint of progression free survival and the duration of response will be analyzed using the Kaplan-Meier method.

14.3.2.2.3 *The Analysis of Correlative Obejctives*

To identify potential predictive biomarkers beyond the genomic alteration, exploratory analysis of gene expression and DNA mutations will be analyzed to associated with ORR and PFS. In this exploratory analysis, the association of DNA mutations in genes and pathways of interest with ORR and PFS will be performed using logistic regression, and Cox regression model. High-dimensional data in these regression models will be dealt using Lasso and Elastic-Net Regularized Generalized Linear Models (glmnet package in R) For gene expression, differential expression between responders and non-responders will be identified using the DESeq package in R.

Plasma concentrations of LY3214996, abemaciclib and its metabolites will be summarized using descriptive longitudinal and statistics. Further PK/PD analyses will be analyzed using linear mixed effect model, in particular, the AUC will be estimated and summarized. However, all of these analyses will be exploratory.

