 14.3.2 Efficacy Analyses48

15 Patient Consent and Peer Judgement.....49

16 References50

List of Tables

Table	Page
Table 2.1 Schedule of Activities.....	11
Table 3.1 Summary of Phase I DLTs.....	20
Table 3.2 Summary of Related TEAEs in >10% of the patients (total)	21
Table 4.1 Objectives	21
Table 8.1 Management Recommendations for Skin Reactions	31

List of Appendices

Appendix		Page
Appendix 1	Abbreviations and Definitions	55
Appendix 2	Study Governance, Regulatory, and Ethical Considerations	58
Appendix 3	Creatinine Clearance Formula	60
Appendix 4	Dose Modification of LY3214996 & Abemaciclib	61
Appendix 5	Sensitive CYP3A Substrates and Narrow Therapeutic Range Drugs.....	66
Appendix 6	Patient Dosing Instructions and Diary	67

1 Synopsis

TITLE	A Phase 2 basket trial of an ERK1/2 inhibitor (LY3214996) in combination with abemaciclib for patients whose tumors harbor pathogenic alterations in BRAF, RAF1, MEK1/2, ERK1/2, and NF1.
PHASE	2
OBJECTIVES	
Primary Objective:
 
 To evaluate the proportion of patients with objective response to an ERK1/2 inhibitor (LY3214996) in combination with abemaciclib for patients whose tumors harbor pathogenic alterations in BRAF, RAF1, MEK1/2, ERK1/2, and NF1 
Secondary Objective:
 
 To evaluate the safety and tolerability of LY3214996 + abemaciclib as defined by CTCAE v5 criteria. To evaluate the median progression-free survival (PFS). To evaluate the duration of response (DOR). 
Correlative Objectives:
 
 To identify potential predictive biomarkers beyond the genomic alteration by which treatment is assigned and/or resistance mechanisms. To evaluate pharmacokinetic parameters of LY3214996 and abemaciclib.
STUDY DESIGN	Single arm, non-randomized, open-label
TOTAL NUMBER OF SUBJECTS	35

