3.2.1.6 Single-Agent Clinical Activity

Part A (N = 54) included patients with CRC (44.4%), NSCLC (5.6%), breast cancer (1.9%), ovarian (3.7%), PDAC (14.8%), and other (29.6%). Of these, 23 had *KRAS* mutations, 10 *NRAS* mutations, and 18 with *BRAF* mutations. At time data presentation, 41 patients have evaluable disease. No partial responses were seen. 13 patients had stable disease and 28 with progressive disease. Notably, some patients with *BRAF* or *NRAS* mutations treated at higher doses of LY3214996 (400 mg and 600 mg daily) stayed on treatment longer with stable disease for ≥ 4 months. Further efficacy studies are ongoing as part of the phase 1 JUAB study.

4 Objectives and Endpoints

Table 4.1 shows the objectives of the study.

Table 4.1 Objectives

Objectives
Primary

 To evaluate the proportion of patients with objective response to an ERK1/2 inhibitor (LY3214996) in combination with abemaciclib for patients whose tumors harbor pathogenic alterations in BRAF, RAF1, MEK1/2, ERK1/2, and NF1

Secondary

 To evaluate the safety and tolerability of LY3214996 + abemaciclib as defined by CTCAE v5 criteria. To evaluate the median progression-free survival (PFS). To evaluate the duration of overall response.
Correlative

 To identify potential predictive biomarkers beyond the genomic alteration by which treatment is assigned and/or resistance mechanisms. To evaluate pharmacokinetic parameters of LY3214996 and abemaciclib.

NOTE: For a more complete description of terms and abbreviations, see [Appendix 1](#).

Abbreviations: ORR = overall response rate; PFS = progression-free survival

5 Study Design

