10.4 Genomics

10.4.1 Whole Blood and Tumor Samples for Genomic Biomarker Research

A whole blood sample will be collected for germline genomic analysis as specified in [Section 2](#).

Using DNA from the tumor biopsy at screening and progression (along with the aforementioned blood germline control), we plan to perform next-generation whole-exome sequencing. The results will serve two purposes: 1) to compare the mutational profile of a tumor biopsy at progression compared to the baseline tumor mutational profile to identify potential acquired mutations driving resistance and 2) to provide mutational data to help identify potential novel biomarkers of response in the form of genomic aberrations either within the RAS/REF/MEK/ERK pathways and/or potentially other cancer pathways. Sequencing will be performed at Indiana University using the Illumina NovaSeq 6000 at our Center for Genomics

and Bioinformatics. Samples will not be used to conduct unspecified disease or population genetic research either now or in the future.

All samples will be coded with the patient ID and sample ID. These samples and any data generated can be linked back to the patient only by the study site personnel. Samples will be retained for a maximum of 15 years after the last patient visit for the study, or for a shorter period if local regulations and/or ethical review boards (ERBs) impose shorter time limits, at a facility selected by Lilly. This retention period enables use of new technologies, response to questions from regulatory agencies, and investigation of variable response that may not be observed until later in the development of LY3214996 or after LY3214996 becomes commercially available.

Molecular technologies are expected to improve during the 15 year storage period and therefore cannot be specifically named. However, existing technologies include whole genome and exome sequencing, genome-wide association studies, multiplex assays, candidate gene studies, and epigenetic analyses. Regardless of the technology utilized, data generated will be used only for the specific research scope described in this section.

Detailed sample collection, shipping, and storage instructions are included the Laboratory Manual.

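### The biomarker objective asks what adds to the qualifying alteration, but the planned analyses name no term for alteration group

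*Combined protocol and SAP*

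**What the plan says.** The Synopsis and Table 4.1 give the first correlative objective: "To identify potential predictive biomarkers beyond the genomic alteration by which treatment is assigned and/or resistance mechanisms".

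Section 14.3.2.2.3 gives the only analysis for it. For mutations, the "association of DNA mutations in genes and pathways of interest with ORR and PFS will be performed using logistic regression", together with a Cox model. For many candidates, "High-dimensional data in these regression models will be dealt using Lasso and Elastic-Net Regularized Generalized Linear Models". For expression, "differential expression between responders and non-responders will be identified using the DESeq package in R". No covariate, stratum, unpenalised term or design factor for the qualifying alteration is named. The section calls this work exploratory.

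Section 10.4.1 plans whole-exome sequencing and looks for response markers among "genomic aberrations either within the RAS/REF/MEK/ERK pathways and/or potentially other cancer pathways". The qualifying genes can therefore be among the candidates.

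Section 14.1 defines four alteration groups: BRAF V600E; non-V600E BRAF with RAF1; MEK1/2 with ERK1/2; and NF1. It uses them for futility: "We will use the Bayesian posterior probability to monitor the response rates for those subgroups". A group stopped for futility is excluded from the final analysis. The documents do not say whether that exclusion reaches the biomarker work.

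The Synopsis describes the design as "Single arm, non-randomized, open-label".

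**The concern.** Whether a marker adds to the alteration is a question conditional on alteration group. The specified analyses are marginal: they relate markers to outcome across the pooled trial. The two agree only if outcome does not vary by group, or if the marker is unrelated to group. Section 14.1 allows each group to be closed separately, so the plan at least provides for response to differ. Mutation and expression profiles may well differ between, say, NF1-altered and BRAF V600E tumours.

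Where both differ, a proxy for the responsive group looks like a discovery, and the qualifying alteration can itself be selected. The objective would then appear to be met by something already known at entry.

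The word predictive raises a second difficulty. With one arm there is no treatment-by-marker interaction to estimate, so an association with PFS may be prognostic only.

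**Working it through.** **The plan's own figures (Section 14.1).** With n = 28 and success at 4 or more responses, P(X ≥ 4 | 28, 0.05) = 0.0491 and P(X ≥ 4 | 28, 0.19) = 0.8065. Accrual is 28 / (1 − 0.20) = 35. The design reproduces. Expected responders are 28 × 0.19 = 5.3 under the alternative and 28 × 0.05 = 1.4 under the null. The biomarker analysis states no figure of its own.

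**Assumptions.** The documents give no group sizes, group response rates or marker frequencies. I assume four groups of 7, a binary marker with no effect on response inside any group, and two-sided 0.05. The futility rule is ignored.

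**Why the pooled comparison is distorted.** With equal groups, response rate p_g and marker prevalence q_g:
- pooled response in marker-positives = Σ q_g p_g / Σ q_g
- pooled response in marker-negatives = Σ (1 − q_g) p_g / Σ (1 − q_g)

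For rates 60/5/5/5% and prevalence 80/10/10/10%:
- positives: (0.8 × 0.60 + 3 × 0.1 × 0.05) / 1.1 = 0.495 / 1.1 = 45%
- negatives: (0.2 × 0.60 + 3 × 0.9 × 0.05) / 2.9 = 0.255 / 2.9 = 9%

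The pooled contrast is 45% against 9%, although within every group it is zero.

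**How often it is flagged.** The unadjusted test is Fisher's exact test on the pooled table. The stratified test uses T = Σ a_g, the responders who carry the marker summed over groups. Each a_g is hypergeometric given its group's margins, and the distributions are convolved. The rates are simulated and vary by a point or two between runs.

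| Group response rates | Marker prevalence | Unadjusted | Stratified |
|---|---|---|---|
| 60/5/5/5% | 80/10/10/10% | about 47–48% | about 1% |
| 50/10/10/6% | 70/15/15/15% | about 18–19% | about 1–2% |
| 35/15/15/11% | 70/15/15/15% | about 7% | about 1–2% |
| 30/15/15/16% | 80/10/10/10% | about 6% | about 1% |
| 31/15/15/15% | 50/25/25/25% | about 3% | about 1–2% |
| 19% in every group | 80/10/10/10% | about 2% | about 1% |

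Each set of rates averages about 19%, the design alternative. If the marker is the qualifying alteration of the responsive group (rates 50/10/10/6%), it is flagged in about 59% of trials unadjusted and 0% stratified. The zero is by construction, since such a marker does not vary within a group.

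**What conditioning costs.** Take a genuine marker concentrated in one group: prevalence 70/15/15/15%, raising response from 20% to 65% in that group and from 3% to 30% elsewhere. Power falls from about 74% pooled to about 26% stratified.

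**The case against.** The other side has several good points.

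**The gap is one of specification.** A reader might infer that the models contain no alteration term and that proxies will be reported as new. The documents do not support that. Section 14.3.2.2.3 is a short outline with an open candidate list, and Section 10.4.1 lets pathway genes in as candidates, so the alteration could enter a model. What stands is that nothing keeps it there, and that the expression comparison names no covariate.

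**The plan already hedges.** It calls the markers potential, the work exploratory and the result an association. A reader might infer that prognostic markers will be labelled predictive, but that is a forecast about reporting. Still, an exploratory label warns of chance findings; it does not make a marginal model answer a conditional question.

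**Heterogeneity is not predicted.** A reader might infer that the plan expects response to differ by group. Section 14.1 gives all four groups the same prior and the same 5% threshold, and tests one pooled rate. Monitoring guards against heterogeneity without forecasting it.

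**The large rates need extreme inputs and sit poorly with the futility rule.** By Section 14.1 a group stops after no responses in 5. At a 5% rate that has probability 0.95^5 = 77%. All three low groups then pass their first look with probability 0.226^3, about 1%; for 10/10/6% it is about 4%. Seven patients in every group would thus be unusual in the strong scenarios. If stopped groups also left the biomarker analysis, much of the contrast between groups would go with them; if they stayed, it would remain in smaller groups. The documents do not settle which. The check also uses one binary marker and an exact test as a stand-in for the planned models.

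**Pooled screening has merit.** With about 5 responders, conditioning can discard real signals, as the power figures show. Tumour type is another plausible confounder in a basket trial, and conditioning on alteration group does not remove it. Both points stand, and they argue for adding the conditioned analysis beside the pooled one.

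**Conclusion.** The point holds as a minor gap in an exploratory analysis. The objective is conditional on the qualifying alteration, and the analyses specified for it name no term for that alteration. Followed as written, they can present a proxy for a responsive group, or the alteration itself, as a new marker.

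The size is conditional. About 18–48% of trials would flag such a proxy under assumed strong heterogeneity, about 3–7% under milder heterogeneity and about 2% under none; stratification holds it at about 1–2%. Group sizes, response rates and prevalences are all assumed, and the futility rule is left out.

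Separately, a single arm cannot show that a marker is predictive and not merely prognostic. A reader might go further and doubt the trial's efficacy conclusions. Nothing here supports that: the primary and secondary endpoints, the sample size and the decision rule do not depend on this analysis.

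**What to change.** Amend Section 14.3.2.2.3 as follows.

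1. Keep the pooled analyses as a screen. For every marker carried forward as adding to the qualifying alteration, report beside it a result conditioned on the four-level group of Section 14.1: an exact or conditional test for response, a Cox model stratified by group for PFS, group as an unpenalised term in glmnet, and group in the DESeq design.
2. Keep the qualifying genes as candidates. Removing them would discard co-occurring and acquired pathway alterations that Section 10.4.1 sets out to study.
3. Describe findings as associated with outcome on treatment.
4. State whether groups stopped for futility stay in this analysis.

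The text change is a few lines, and the group follows from the sequencing required by inclusion criterion 3 in Section 6.1. The real cost is sensitivity. With about 5 expected responders, three group terms plus a marker will not fit reliably in ordinary logistic regression, and a group without responders adds nothing to a conditional test of response. Exact or penalised-likelihood methods are needed. The plan should say that power is low, especially for markers concentrated in one group.
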